2.2.2.7 Relative Bioavailability Study

Recently, a tablet formulation was developed for VTX002, and a relative bioavailability study was performed comparing the relative bioavailability of the 20 mg tablet to 20 mg of the free base suspension used in the Phase 1 study. The ratio of the AUC_{0-t} for the tablet compared with the suspension was [REDACTED]. For the low dose in this study of 30 mg daily, that is equivalent to [REDACTED] of the free base suspension used in the Phase 1 study, and the high dose of 60 mg daily is equivalent to [REDACTED] of the free base suspension. Based on the similarity in PK characteristics (C_{max} and AUC) of the suspension and tablet formulation and a half-life of approximately 20 hours, it is presumed that as with the suspension formulation, there would be minimal effect of food on exposure to the VTX002 tablet formulation.

2.3 Benefit/Risk Assessment

VTX002 may benefit patients with moderately to severely active UC whose disease has progressed or is unresponsive to currently approved standard of care agents. Nonclinical results suggest that VTX002 administration would result in reduced circulating lymphocytes in vivo, and efficacy was demonstrated in a model of colitis in the rat. Results from the Phase 1 study demonstrated a strong relationship between dose, exposure, and lowering of circulating lymphocyte levels.

Potential risks for study participation have been associated with VTX002 include the following:

Decreased Heart Rate and/or Atrioventricular Conduction

- Guidance for cardiac monitoring is provided, including first dose and extended cardiac monitoring postdose as needed. On Day 1 and OLE Day 1 (OLE Week 0/OLE Visit 1), following the first dose of study drug, participants will remain in the clinic for 6 hours to monitor vital signs and cardiac conduction. Upon release from the clinic, participants will be monitored closely throughout study participation (see [Section 6.5](#)).
- A dose titration schedule will be implemented to minimize the risk for cardiovascular events related to administration of the first dose of study treatment ([Section 6.2](#)).
- Availability of emergency equipment should be within close proximity to study site. Personnel experienced in the use of advanced life support must be readily accessible during the first-dose monitoring and reinitiation of treatment, as well as in case of an emergency (see [Section 6.5](#)).
- Criteria for study treatment discontinuation are outlined in [Section 7.0](#).

Infections

- Given the mechanism of action of decreased peripheral lymphocytes, VTX002 may increase the risk of infections, including opportunistic infections. Participants should be monitored for signs and symptoms of infection during the study and throughout the Follow-Up Period. Participants with active acute or chronic infection should not be enrolled. Participants who develop an active infection during the study should be monitored and may need to have study treatment temporarily discontinued ([Section 7.0](#)).

Macular Edema

- Although not observed in any of the VTX002 preclinical safety or clinical Phase 1 studies, treatment with agents in the same class have been associated with cases of macular edema, with or without visual symptoms. As described in [Section 8.4.6](#) of the protocol, participants should be monitored for visual symptoms during the study, and, if symptoms develop, an ophthalmologic evaluation and optical coherence tomography (OCT) should be performed.

Decrease in Pulmonary Function

- Although not observed in any of the VTX002 preclinical safety studies or clinical Phase 1 studies, treatment with agents in the same class have been associated with a decrease in pulmonary function. As described in [Section 8.4.5](#) of the protocol, participants should be monitored for dyspnea and other pulmonary symptoms, and, if pulmonary symptoms develop, a PFT, including diffusing capacity of lung for carbon monoxide, should be performed.

Drug-Drug Interactions

In vitro studies suggested that VTX002 may be an inhibitor of P-glycoprotein (P-gp) and breast cancer resistance protein (BCRP) transporters. As described in [Section 6.10.2](#), therapies that are substrates or inhibitors of P-gp and BCRP are prohibited.

In addition, risk for reproductive and developmental toxicity cannot be excluded; thus, inclusion/exclusion criteria regarding pregnancy are noted to mitigate this risk (see [Section 5.0](#)). The risk for reproductive and developmental toxicity has also been observed for all other approved S1P receptor modulators.

Results from preclinical safety studies showed that VTX002 has a low risk of phototoxicity. Participants may be evaluated for any signs of phototoxicity as part of the PE.

The Sponsor will immediately notify the Investigator if any additional safety or toxicology information becomes available during the study.

Other risks for study participation may include treatment with placebo and a potentially ineffective treatment, and delay of treatment with other approved medicinal products. For vulnerable populations as geriatric patients, risks for study participation should be considered, given the potential higher number of comorbidities and concomitant medications that may be present in this population. Ultimately, the Investigator should consider if the benefits outweigh the risks for patients to participate in this study.

More detailed information about the known and expected benefits and risks and reasonably expected AEs of VTX002 may be found in the Investigator's Brochure.⁷

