3.3 Endpoint Definitions

Clinical remission: stool frequency (SF) subscore = 0 or 1, RB subscore = 0, and endoscopic subscore (ES) ≤ 1 (excluding friability)

Clinical response using MMS: A ≥ 2 -point and $\geq 30\%$ decrease from baseline in MMS, and a ≥ 1 -point decrease from baseline in RB subscore or an absolute RB subscore ≤ 1

Clinical remission using total MCS: Total MCS ≤ 2 points with no individual subscore > 1 point (SF subscore = 0 or 1, RB subscore = 0, ES ≤ 1 [excluding friability], Physician Global Assessment [PGA] ≤ 1 , and SF + RB + ES + PGA ≤ 2)

Clinical response using total MCS: A ≥ 3 -point and $\geq 30\%$ decrease from baseline in total MCS, and a ≥ 1 -point decrease from baseline in RB subscore or an absolute RB ≤ 1 .

Endoscopic improvement: ES ≤ 1 (excluding friability)

Endoscopic remission: ES = 0

Histologic improvement: Geboes Index score < 3.1 . Histology will also be assessed by the Robarts Histopathology Index and Nancy Index.

Histologic remission: Geboes Index score < 2.0 . Histology will also be assessed by the Robarts Histopathology Index and Nancy Index.

Endoscopic improvement-histologic remission: $ES \leq 1$ (excluding friability) and histologic remission measured by a Geboes Index score < 2.0

Endoscopic and histologic remission: $ES = 0$ and histologic remission measured by a Geboes Index score < 2.0

Histologic-endoscopic mucosal improvement (HEMI): $ES \leq 1$ (excluding friability) and histologic remission measured by a Geboes Index score < 3.1

Symptomatic remission: SF subscore = 0 or 1 and RB subscore = 0

Symptomatic response: Decrease from baseline $\geq 30\%$ of the combined RB and SF subscores

Endoscopic and clinical remission: SF subscore ≤ 1 , RB subscore = 0, and $ES = 0$

Endoscopic, histologic, and clinical remission: SF subscore ≤ 1 , RB subscore = 0, $ES = 0$, and histologic remission measured by a Geboes Index score < 2.0

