6.10 Prior and Concomitant Therapy

All concomitant medications, including over-the-counter or prescription medicines, blood products, vaccines, vitamins, holistic products, and radiotherapy, will be collected from Screening through the 2-Week Follow-Up visit and recorded in the eCRF. Any medication given for a study-related AE should be recorded from the time of informed consent.

The Medical Monitor should be contacted if there are any questions regarding concomitant or prior therapy. Medication history should be collected for at least 4 weeks prior to Screening.

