6.10.2 Prohibited Medications

In vitro studies suggested that VTX002 may be an inhibitor of P-gp and breast cancer resistance BCRP transporters ([Section 2.3](#)). Any necessary concomitant use of any of the following must be discussed with Medical Monitor.

- P-gp transporter substrates or inhibitors: amiodarone, carvedilol, clarithromycin, cyclosporine, dabigatran etexilate, digoxin, dronedarone, fexofenadine, itraconazole, ketoconazole, lapatinib, loperamide, lopinavir, propafenone, quinidine, ranolazine, reserpine, ritonavir, saquinavir, tacrolimus, talinolol, telaprevir, tipranavir, verapamil, vinblastine
- BCRP transporter substrates or inhibitors: coumestrol, curcumin, cyclosporine A, daidzein, dantrolene, eltrombopag, estrone-3-sulfate, genistein, novobiocin, prazosin, rosuvastatin, sulfasalazine

The following concomitant medications/therapy are prohibited for the entire duration of the study:

- Treatments for UC other than those listed in the eligibility criteria (see [Section 5.1](#) and [5.2](#))
- Chronic nonsteroidal anti-inflammatory drug (NSAID) use (Note: Occasional use of NSAIDs and aspirin up to 325 mg/day is permitted)
- Marketed biologic therapies

- Immunosuppressive agents (eg, AZA, 6-MP, tofacitinib)
- Any per rectum therapy including enemas (eg, 5-ASA, corticosteroid), other than that required for endoscopy preparation
- Treatment with cyclosporine, tacrolimus, sirolimus, methotrexate, or mycophenolate mofetil
- Cholestyramine or other drug interfering with enterohepatic circulation unless the dose has been stable for > 6 months prior to Screening
- S1P receptor modulators including but not limited to fingolimod, siponimod, ozanimod, ponesimod, and etrasimod
- Receipt of a live vaccine from 4 weeks prior to randomization and/or until 2 weeks post last dose. Nonlive vaccines, including SARS-CoV-2, can be administered according to local vaccination standards.
- Treatment with lymphocyte-trafficking inhibitors
- Treatment with lymphocyte-depleting therapies (eg, alemtuzumab, anti-CD4, cladribine, rituximab, ocrelizumab, cyclophosphamide, mitoxantrone, total body irradiation, bone marrow transplantation, daclizumab)
- Treatment with D-penicillamine, or thalidomide, dimethyl fumarate, or pyrimidine synthesis inhibitors

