3.5 Estimands

The primary and key secondary estimands are described in Table 1 below. The analyses will be performed on the Full Analysis Set (FAS) as defined in [Section 8](#). Other Secondary and Exploratory efficacy endpoints (specified in [Sections 16.3](#) and [16.4](#)) will generally be subject to the population, intercurrent event handling strategy, and population-level summary measures similar to the primary estimand. Supplementary analyses for the primary and key secondary

estimands will be performed using the FAS, Modified Full Analysis Set (mFAS), and Per Protocol (PP) populations.

Intercurrent events include exposure to rescue therapy for UC – see [Section 25](#), Appendix IV for the list of rescue therapies applying to this study. Additional intercurrent events include missed endoscopy at Visit 7 Week 13 for participants available to have a Visit 7 Week 13 endoscopy, and study discontinuation for either disease worsening or treatment-emergent adverse event with a preferred term indicating ulcerative colitis. See [Sections 16](#), [16.1.2](#), and [29](#) (Appendix VIII).

Participants will be evaluated for exposure to rescue therapy by Ventyx reviewers according to the guidelines presented in [Section 25](#), Appendix IV. Participants deemed to have received rescue therapy, and not experiencing other deviations preventing contribution to the primary and key secondary analyses of the primary and key secondary efficacy endpoints, will be treated as non-responders in those analyses; they will also be included in the Per Protocol analysis set. Use of concomitant medications and procedures that are not potentially effective for the treatment of UC will not be considered intercurrent events.

Table 1. List of Primary and Key Secondary Estimands

Estimand	Definition	Attributes			
		Population	Variable / Endpoint	Primary Intercurrent Event Handling Strategy	Population-Level Summary Measure
Primary Estimand	Efficacy of VTX002 on Clinical Remission (Modified Mayo Score) at Week 13	FAS	Proportion of participants with stool frequency (SF) subscore = 0 or 1, rectal bleeding (RB) subscore = 0, and endoscopic subscore (ES) \leq 1 (excluding friability)	Participants with any intercurrent events prior to Week 13 efficacy assessment will be treated as non-responders	Difference between VTX002 and Placebo with respect to population proportion of clinical remission at Week 13

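### Loperamide is banned in one protocol section and conditionally allowed in another, and the SAP has no rule for it, so stool frequency reached on an antidiarrheal can count towards remission

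*Protocol*

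**What the plan says.** **Protocol on use.** Section 2.3 (Drug-Drug Interactions) says that "therapies that are substrates or inhibitors of P-gp and BCRP are prohibited" and refers to Section 6.10.2. That section is headed as a list of prohibited medications, but its rule for the transporter drugs is softer: "Any necessary concomitant use of any of the following must be discussed with Medical Monitor". It sets no time or criterion for the discussion. The P-gp list includes "lapatinib, loperamide, lopinavir, propafenone". A separate list of drugs banned for the whole study follows; it names no antidiarrheal. Its nearest entry is "Treatments for UC other than those listed in the eligibility criteria". Section 6.10 requires recording of "All concomitant medications, including over-the-counter or prescription medicines".

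**Endpoints.** Protocol 3.3 has "Symptomatic remission: SF subscore = 0 or 1 and RB subscore = 0". Clinical remission, the primary endpoint, adds ES of 1 or less. SF comes from the participant's daily stool count in the eDiary (Protocol 8.3.1), averaged over a 7-day look-back (SAP 10.3). Symptomatic remission on 60 mg is formally tested in Family 2 (SAP 10.4).

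**SAP on non-response.** SAP 16 names three intercurrent events that make a participant a non-responder: a missed Week 13 endoscopy, leaving the study in Induction for worsening or a UC adverse event, and rescue therapy. For rescue, SAP 3.5 points to "Appendix IV for the list of rescue therapies applying to this study". That appendix works through named products in fixed classes: biologics, immunosuppressants, 5-ASA, small molecules, glucocorticoids, apheresis and surgery. SAP 3.5 adds: "Use of concomitant medications and procedures that are not potentially effective for the treatment of UC will not be considered intercurrent events". SAP 14.2 flags P-gp and BCRP drug use in datasets and listings, without consequence for response.

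**The concern.** Two sites can give opposite answers about loperamide and both cite the protocol. Once it has been taken, the SAP does not deal with it. New or increased steroid use beyond the Appendix IV limits, or a 5-ASA change from baseline, makes a participant a non-responder; a drug that acts directly on an endpoint component does not. Symptomatic remission has only two components, and SF is one of them.

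The bias could run either way. If use follows symptoms, it may be heavier on placebo and dilute the observed difference. Similar use in both arms raises both rates. The documents do not say which applies, and no planned analysis is directed at it.

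**Working it through.** **Step 1: follow one participant through the plan.** Suppose a participant takes loperamide during the 7 days before bowel preparation for the Week 13 endoscopy and records SF 0 or 1 and RB 0.

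| Question | Where | Answer |
|---|---|---|
| Was the use allowed? | Protocol 2.3 | No |
| Was the use allowed? | Protocol 6.10.2 | Yes, if necessary and discussed with the Medical Monitor |
| Is SF adjusted or set to missing? | SAP 10.3 | No antidiarrheal rule |
| Is it rescue therapy? | SAP Appendix IV | Not among the named products |
| Is it another intercurrent event? | SAP 16 | Not in itself |
| Does the P-gp flag change response? | SAP 14.2 | No |

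The participant is a symptomatic remitter in the Full Analysis Set, and a clinical remitter if ES is 1 or less. The result is the same whether the use was approved or went undetected.

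**Step 2: reproduce the plan's power.** Inputs from Protocol 9.2 and SAP Appendix VII: 28% vs 8%, 57 per group, two-sided 5%, chi-squared test by normal approximation. With p̄ the mean of the two proportions,

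power = Φ{ [|p1 − p2|·√n − 1.96·√(2p̄(1 − p̄))] / √(p1(1 − p1) + p2(1 − p2)) }

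= Φ{ [0.20 × 7.550 − 1.96 × √0.2952] / √0.2752 } = Φ{ (1.510 − 1.065) / 0.525 } = Φ(0.85) = 0.802, as the SAP reports.

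**Step 3: illustrate, varying both unknowns.** The documents give neither the share of participants using loperamide in the window nor the share of those users who would otherwise fail on SF alone. Both are assumptions. Shift in the clinical remission rate = use × share.

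| Use | Share failing on SF alone | Shift (points) | Power, shift on placebo only | Power, same shift in both arms |
|---|---|---|---|---|
| 5% | 5% | 0.25 | 78.9% | 79.8% |
| 10% | 5% | 0.50 | 77.6% | 79.3% |
| 15% | 5% | 0.75 | 76.3% | 78.9% |
| 5% | 20% | 1.0 | 74.9% | 78.5% |
| 10% | 20% | 2.0 | 69.2% | 76.8% |
| 15% | 20% | 3.0 | 63.3% | 75.2% |

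The table concerns the primary endpoint, the only one for which the plan states rates. A 20% share means that one user in five already has RB 0 and a centrally read ES of 1 or less and fails only on SF. That is 2.5 times the assumed placebo remission rate (20/8). For symptomatic remission the share could be larger, because there is no ES condition, but no planning rate exists from which to compute an effect.

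**The case against.** The defence has real substance.

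- **Casual use is not permitted.** A reader might infer that the plan lets participants take over-the-counter loperamide freely. It does not: use without a Medical Monitor discussion breaches 6.10.2, and loperamide taken for UC diarrhea could also fall under the ban on other UC treatments. The gap is confined to approved or undetected use.
- **A route to non-response exists.** Under Protocol 7.1 the Investigator may treat administration of a prohibited UC medication in Induction as worsening and stop study treatment. If the participant then leaves the study for worsening, SAP 16 makes that a non-response. The route is discretionary, and it depends on loperamide being read as a prohibited UC medication.
- **The Per Protocol analysis might remove users.** It is run for the primary and all key secondary endpoints (SAP 16.1.6 and Table 6). It excludes deviations that prevent contribution to the primary analysis, and nothing says whether loperamide use is one.
- **RB and ES protect the primary endpoint.** This largely stands. Loperamide cannot turn a participant with bleeding or ES of 2 or more into a clinical remitter.
- **A false-positive risk is not shown.** Because VTX002 may inhibit P-gp, a reader might infer that loperamide acts more strongly on VTX002 and inflates the type I error. The only basis is an in vitro suggestion, and no document links it to stool frequency. If loperamide acts equally in both arms and there is no true effect, the two rates stay equal and the test keeps its level.

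**Conclusion.** The point holds as an inconsistency between Protocol 2.3 and 6.10.2, together with a missing antidiarrheal rule in the SAP. Loperamide use in the look-back window can be counted towards symptomatic remission and, less often, clinical remission. Non-response follows only through a discretionary discontinuation for worsening, and Per Protocol exclusion is uncertain.

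The main exposure is symptomatic remission. Direction and size cannot be established from the documents. A reader might take the 63.3% in the table as the expected loss of power; it is not. It needs 15% use, a 20% share and an effect on placebo alone, none of which the documents support. The conclusion relies on one fact from general pharmacology that the documents do not state: loperamide reduces stool frequency. This is an inexpensive improvement worth considering, not a flaw that undermines the primary analysis.

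**What to change.** 1. **Protocol 6.10.2.** Take loperamide off the list of drugs to discuss. Add a separate sentence, outside the list that applies for the entire study: antidiarrheals (eg, loperamide) must not be started or increased from Screening through the Week 13 visit, and must not be taken during the 7-day diary look-back before bowel preparation for the Week 13 endoscopy. State there too what interaction precaution applies to loperamide after Week 13, so that removing it from the list leaves no gap.
2. **SAP, before the interim database lock.** For clinical remission and symptomatic remission at Week 13, prespecify an analysis in which any antidiarrheal use recorded within the 7-day SF look-back is a non-response. This can be an Appendix IV entry or at least a sensitivity analysis. If it goes into Appendix IV, limit it explicitly to these two endpoints at that visit, because SAP 16 otherwise carries an intercurrent event into all responder analyses at later timepoints.
3. **Protocol 2.3 and 6.10.2.** State the same rule in both places for the remaining P-gp and BCRP drugs. If that rule is discussion with the Medical Monitor, it should take place before randomization, or before the drug is started if that is later.

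The cost is a few sentences and one programmed analysis. Over-the-counter medications are already recorded, so no new data, visits or participants are needed. If enrollment is too far advanced for the protocol edits, item 2 alone closes the analysis gap for recorded use. The downside is that a few participants may become non-responders and that loperamide for symptoms is restricted for 13 weeks.

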3.0 OBJECTIVES AND ENDPOINTS

This is a Phase 2, multicenter, randomized, double-blind, placebo-controlled, parallel-group study to evaluate the clinical efficacy and safety of VTX002 in participants with moderately to severely active UC.

3.1 Objectives

Primary Objective

- Assess the efficacy of VTX002 when administered for 13 weeks on clinical remission

Secondary Objectives

- Assess the efficacy of VTX002 when administered for 13 weeks on endoscopic changes, symptomatic response and remission, histology, and mucosal healing
- Assess the safety and tolerability of VTX002
- Assess the PK of VTX002

Long-Term and Open-Label Extension Objectives

- Assess the efficacy of VTX002 through the Long-Term Extension (LTE) and Open-Label Extension (OLE) Treatment Periods on endoscopic changes, symptomatic response and remission, histology, and mucosal healing
- Assess the safety of VTX002 through the LTE and OLE Treatment Periods

Exploratory Objectives

- Assess the effect of VTX002 on health-related quality of life (HRQoL) outcomes and biomarkers

3.2 Endpoints

The endpoints for the study are listed below, and definitions are provided in [Section 3.3](#). The primary and four key secondary endpoints will be tested for superiority of VTX002 60 mg vs placebo and VTX002 30 mg vs placebo. The remaining endpoints will be presented descriptively. Details of the statistical plan are presented in [Section 9.0](#).

Primary Endpoint

- The proportion of participants with clinical remission at Week 13 using modified Mayo score (MMS)

Key Secondary Endpoints

- The proportion of participants with endoscopic improvement at Week 13
- The proportion of participants with symptomatic remission at Week 13

- The proportion of participants with histologic remission at Week 13
- The proportion of participants with endoscopic improvement-histologic remission at Week 13

Other Secondary Endpoints

- The proportion of participants with clinical response using MMS at Week 13
- The proportion of participants with endoscopic remission at Week 13
- The proportion of participants with endoscopic and histologic remission at Week 13
- The proportion of participants with endoscopic and clinical remission at Week 13
- The proportion of participants with endoscopic, histologic, and clinical remission at Week 13
- The proportion of participants with symptomatic remission at Weeks 4, 8, 10
- The proportion of participants with symptomatic response at Weeks 4, 8, 10, 13
- The proportion of participants with clinical remission using total Mayo Clinic score (MCS) at Week 13
- The proportion of participants with clinical response using total MCS at Week 13
- The proportion of participants with histologic improvement at Week 13
- Proportion of participants with any decrease from baseline in Geboes Index score at Week 13
- The proportion of participants with histologic-endoscopic mucosal improvement (HEMI) at Week 13
- The proportion of participants with UC-related hospitalizations
- The proportion of participants requiring UC-related surgeries, including colectomy
- Plasma concentrations of VTX002, assessed from samples collected predose at Weeks 0, 1, 4, 8, and 13 in the Induction Treatment Period, and Weeks 18, 26, 36, and 52 in the LTE Treatment Period; at the 1-Week and 2-Week Follow-Up visits; and at 2, 4, and 6 hours (\pm 15 minutes) postdose at Week 0

Safety Endpoints

- Incidence and severity of AEs
- Incidence and severity of laboratory abnormalities, and change from baseline in laboratory values (eg, hematology and serum chemistry)
- Incidence of clinically significant vital sign abnormalities and changes from baseline

Exploratory Endpoints

The endpoints described here will be analyzed separately for the Induction Treatment Period, LTE Treatment Period, and OLE Treatment Period. OLE analyses will be described in detail in the Statistical Analysis Plan (SAP).

- Proportion of participants with clinical remission after 52 weeks of treatment
- Proportion of participants with clinical remission after 13 and 52 weeks of treatment
- Proportion of participants with symptomatic remission at Weeks 18, 26, 36, and 52
- Proportion of participants with endoscopic and histologic remission after 52 weeks of treatment

- Proportion of participants with endoscopic improvement-histologic remission after 52 weeks of treatment
- Proportion of participants with endoscopic and clinical remission after 52 weeks of treatment
- Proportion of participants with endoscopic, histologic, and clinical remission after 52 weeks of treatment
- Proportion of participants with HEMI after 52 weeks of treatment
- Proportion of participants with clinical response after 52 weeks of treatment
- Proportion of participants with symptomatic response at Weeks 18, 26, 36, and 52
- Proportion of participants with symptomatic response at OLE Week 13, and at each additional OLE visit
- Proportion of participants with any decrease from baseline in Geboes Index score at Week 52
- Change from baseline in fecal calprotectin (FCP) at Weeks 1, 4, 8, 13, 26, 36, 52, and at visits during the OLE
- Change from baseline in C-reactive protein (CRP) at Weeks 1, 4, 8, 13, 26, 36, 52, and at visits during the OLE
- Change from baseline in partial Mayo score (PMS) at Weeks 4, 8, 13, 18, 26, 36, 52, and at visits during the OLE
- Change from baseline in total MCS at Week 52
- Change from baseline in Inflammatory Bowel Disease Questionnaire (IBDQ) score at Weeks 13 and 52
- Change and percentage change from baseline in lymphocyte counts at Weeks 1, 4, 8, 13, 26, 36, and 52

